- f Screening chest x-ray does not need to be repeated if a standard-of-care chest x-ray was performed within 72 hours of randomization. Subjects that are outpatient and starting on oral therapy do not need a screening x-ray.
- g Local laboratory; includes hemoglobin*, hematocrit*, white blood cell count with differential*, platelet count*, blood urea nitrogen*, calcium*, serum creatinine, potassium*, sodium*, aspartate aminotransferase, alanine aminotransferase, alkaline phosphatase*, total and direct bilirubin, and albumin*. If laboratories with * designation are not obtained, it will not result in a protocol deviation.
- h A separate study sample is not required if safety labs above are obtained at baseline per standard of care. If multiple laboratory tests are obtained within 72 hours of randomization, record test results closest to randomization.
- i Every effort should be made to obtain safety labs 72 (±24) hours after the first dose to include aspartate aminotransferase, alanine aminotransferase, alkaline phosphatase, total and direct bilirubin, and white blood cell count with differential. A separate study sample is not required if safety labs above are obtained within the visit window per standard of care.
- j Safety labs must be collected on the last day of dosing or within 48 hours after the last dose. A separate study sample is not required if safety labs above are obtained on the last day of dosing or within 48 hours after the last dose per standard of care.
- k Record the safety labs if performed per standard of care; if multiple laboratory tests are obtained on the same day, record test results closest to administration of study drug.
- l Microbiological assessments will be recorded if performed per routine medical care. These include cultures from sterile body fluids and molecular and serologic tests for *Mycoplasma pneumoniae* and *Chlamydia pneumoniae*.
- m Radiological imaging of the chest, including chest x-ray or computed tomography (CT) scan, will be recorded if performed per routine medical care.
- n Non-pharmacologic treatments (such as operative procedures) will be recorded if performed per routine medical care.
- o Female subjects of childbearing potential within 24 hours of first dose.
- p If the screening visit for females occurred greater than 24 hours before receiving the study drug.

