In the pooled Phase 3 CABP studies, rates of bilirubin elevation to levels $>\text{ULN}$ were comparable between solithromycin and moxifloxacin (4.3% vs 4.0%, respectively), and elevations $>2\times\text{ULN}$ were uncommon ($<0.5\%$) in both treatment groups. Solithromycin was more frequently associated with alkaline phosphatase elevation to $>1.5\times\text{ULN}$ than moxifloxacin (5.2% versus 2.9%, respectively), consistent with the potential to induce mild degrees of cholestasis, as has been observed with older macrolides and other antibiotics.

Solithromycin was generally well tolerated in subjects with cirrhosis of Child Pugh Class A, B and C severity in a controlled Phase 1 trial. In the Phase 3 CABP studies, the overall incidence of AEs was similar among subjects with and without hepatic impairment. ALT elevation to $>5\times\text{ULN}$ occurred with identical frequency among patients with and without hepatic impairment (2.4%), and AST elevation $>5\times\text{ULN}$ occurred in 1 patient with baseline hepatic impairment.

Analysis of ALT elevation by patient characteristics including age, sex, race, history of chronic liver disease and concomitant exposure to statins have not revealed a population at particular risk for these events.

While solithromycin can cause asymptomatic, reversible ALT elevation and mild degrees of cholestasis, the overall liver safety profile of clinically important events was comparable to moxifloxacin and may be comparable to the older macrolides.

When solithromycin is taken for longer than 7 days, rare cases of jaundice and itching have occurred. These events were reversible after solithromycin treatment was stopped.

Macrolides have been associated with QT prolongation and risk for torsades de pointes. In March 2013, the FDA warned the public that azithromycin may cause fatal heart rhythm disturbances, particularly in patients with known risk factors. A thorough QT study of solithromycin was negative, demonstrating that solithromycin does not have a propensity to prolong the QT interval in a clinically significant manner in healthy subjects.

In the pooled Phase 3 CABP studies, cardiac AEs were observed more frequently in moxifloxacin recipients (4.7%) than solithromycin recipients (3.0%). Most of these events reflected the underlying chronic diseases of enrolled patients in the context of the severe physiologic stress of CABP and were not considered study drug related.

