10.2 Treatment Period Procedures

10.2.1 Treatment Days up to Last Day of Treatment

1. Every effort should be made to obtain safety labs 72 hours (± 24 hours) after the first dose to include ALT, AST, alkaline phosphatase, total and direct bilirubin, and WBC with

differential. A separate study sample is not required if these labs are obtained at 72 hours (± 24 hours) after the first dose per standard of care.

2. Document physical examination if available per standard of care on the day of clinical outcome assessment only.
3. Document vital signs if available per standard of care on the day of clinical outcome assessment only.
4. Document standard-of-care safety labs as described in Section 10.4.1.
5. Document microbiology assessments as described in Section 10.4.2.
6. Document radiological imaging as described in Section 10.4.3.
7. Document non-pharmacologic treatments on the day of clinical outcome assessment only as described in Section 10.4.3.
8. If the screening visit for females occurred more than 24 hours before receiving the study drug, a pregnancy test will be performed prior to first dose of study drug.
9. Review and record concomitant medications as described in Section 8.3.
10. Administer study drug. If the subject is an outpatient and receiving study drug orally, a dosing diary is included on the capsule blister pack and the label for the suspension. This diary should be completed for each dose taken and brought back to each visit for review and accountability.
11. Obtain PK samples as described in Section 10.4.3.
12. Review and record any AEs and SAEs as described in Section 12.1.
13. Perform clinical outcomes assessment once on days 3–5 (ECR) if the subject is available. A return visit is not required to perform the outcomes assessment.

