10 DATA ANALYSIS

10.1 Safety Evaluations

New events that occur or pre-existing conditions that worsen through frequency or intensity will be reported as AEs or SAEs. The investigator will provide date of onset and resolution, intensity, frequency, action(s) taken, changes in study drug dosing, relationship to study drug, and outcome. Laboratory determinations performed by local laboratories including hematology values (hemoglobin, hematocrit, WBC count with differential, and platelet count) and serum chemistry values (blood urea nitrogen [BUN], calcium, serum creatinine, potassium, sodium, AST, ALT, alkaline phosphatase, total and direct bilirubin, and albumin) are required by the protocol within 72 hours prior to the first dose, and on the last day of study drug. In addition, investigators are asked to make every effort to obtain safety labs (to include aspartate aminotransferase, alanine aminotransferase, alkaline phosphatase, total and direct bilirubin, and white blood cell count with differential) 72 hours (± 24 hours) after the first dose, at the Day 16 and Day 28 post-randomization visits (implemented in Protocol version 3.0).

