10.3.2 Laboratory Data

Descriptive statistics will be generated for post-baseline abnormal laboratory data, such as hematology and serum chemistry values. Additionally, shift tables will be presented. The shift tables tabulate the number of lab values determined to be “Normal” and “Abnormal” at baseline and post-baseline timepoints. The classifications on shift tables will categorize lab values as “Normal” when they are in an acceptable range, using a combination of clinician judgment specific to each lab test, and the local lab reference ranges (see below). Laboratory values outside the normal range will be graded on the Labs Listing as 1x, 2x, 3x, 5x or 10x the upper limit (or .5x, 1x the lower limit) of normal value based on appropriate increases or decreases. Lab tests reflective of liver toxicity (ALT, AST, and Total and Direct Bilirubin) will be further summarized in terms of the most extreme values and largest increases from baseline observed from the start of study drug through Day 16 Post-Randomization (± 4 days). Laboratory data will also be summarized graphically to show the magnitude and changes in individual subject values over time relative to normal ranges.

Laboratory Name	Clinically Pertinent Normal Range
Blood Urea Nitrogen [BUN]	(0, Site Specific ULN)
Calcium	(Site Specific LLN, Site Specific ULN)
Serum Creatinine	(0, Site Specific ULN)
Potassium	(Site Specific LLN, Site Specific ULN)
Sodium	(Site Specific LLN, Site Specific ULN)

AST	(0, Site Specific ULN)
ALT	(0, Site Specific ULN)
Alkaline Phosphatase	(0, Site Specific ULN)
Total Bilirubin	(0, Site Specific ULN)
Direct Bilirubin	(0, Site Specific ULN)
Albumin	(Site Specific LLN, ∞)
Hemoglobin	(Site Specific LLN, ∞)
Hematocrit	(Site Specific LLN, ∞)
WBC Count	(Site Specific LLN, Site Specific ULN)
Platelet Count	(Site Specific LLN, Site Specific ULN)
Neutrophils	(Site Specific LLN, Site Specific ULN)
Lymphocytes	(Site Specific LLN, Site Specific ULN)
Monocytes	(Site Specific LLN, Site Specific ULN)
Eosinophils	(Site Specific LLN, Site Specific ULN)
Basophils	(Site Specific LLN, Site Specific ULN)
C-reactive protein	(0, Site Specific ULN)
Procalcitonin	(0, Site Specific ULN)

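### The SAP liver summary leaves out alkaline phosphatase, so no planned table gives its largest rise from baseline or the count above 1.5x ULN, the level at which the protocol reports an adult excess

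*SAP*

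**What the plan says.** **The adult signal.** Protocol 5.2.4.1 says that ALP above 1.5x ULN was more frequent on solithromycin "than moxifloxacin (5.2% versus 2.9%, respectively), consistent with the potential to induce mild degrees of cholestasis".

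**Collection.** Footnote i to protocol Table 1 reads "Every effort should be made to obtain safety labs 72 (±24) hours after the first dose to include aspartate aminotransferase, alanine aminotransferase, alkaline phosphatase" and continues with bilirubin and the white cell count. It is attached to the 72-hour, Day 16 and Day 28 tests. Protocol 10.2.1, 10.3.1 and 10.3.2 repeat the request and name ALP each time.

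**The waiver.** Footnote g to the same table marks ALP with an asterisk but not ALT, AST or bilirubin: "alanine aminotransferase, alkaline phosphatase*, total and direct bilirubin, and albumin". It then states: "If laboratories with * designation are not obtained, it will not result in a protocol deviation". The footnote is attached to the whole row of study-required safety labs.

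**The SAP.** Section 10.1 lists a panel that includes ALP and says these tests "are required by the protocol within 72 hours prior to the first dose, and on the last day of study drug". SAP Table 4 reproduces footnote g without asterisks. Section 10.3.2 promises the most extreme values and largest increases from baseline, from start of drug through Day 16, for a closed list: "Lab tests reflective of liver toxicity (ALT, AST, and Total and Direct Bilirubin) will be further summarized". ALP appears in that section only in the table of normal ranges.

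**The concern.** Safety is the primary objective, and the protocol's own adult data show a solithromycin excess in ALP that it calls "consistent with the potential to induce mild degrees of cholestasis". Sites were asked for repeat ALP measurements alongside the other liver tests. One would expect ALP to be summarised with them. Instead it is treated as routine chemistry, and the clinical study report would have no table showing how far ALP rose or how many children passed the level used in the adult programme.

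Baseline matters more for ALP than the plan allows. The hepatic exclusion criterion (protocol 8.2, item 7) uses ALT, AST and bilirubin only, so a subject may enter with a raised ALP. Without a baseline, a later high value cannot be classed as new or pre-existing.

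**Working it through.** The documents state no sample size or power figure for ALP, so the main check sets the planned outputs side by side. The reading rests on the text of SAP 10.3.2 and on the output titles in SAP section 12.

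**1. What each output gives for ALP**

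| Planned output | ALP covered? | Largest increase tabulated? | Count above 1.5x ULN tabulated? |
|---|---|---|---|
| Liver summary (10.3.2; Tables 14.4.3.2.4 and 14.4.3.2.5) | No | No | No |
| Chemistry shift (Table 14.4.3.2) | Yes | No, Normal/Abnormal only | No |
| Abnormal chemistry results (Table 14.4.3.2.1) | Yes | No, describes abnormal post-baseline values | No such cut-off stated |
| Worst against baseline (Figures 14.4.3.2.2 and 14.4.3.2.3) | Yes | Plotted, not tabulated | No |
| Chemistry listing (16.2.8.2) | Yes | No | No, grades are 1x, 2x, 3x, 5x and 10x |

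A subject who moves from slightly abnormal to well above 1.5x ULN stays in the Abnormal-to-Abnormal cell of the shift table.

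**2. Protocol against SAP.** Protocol 14.1.3 commits to observed values and changes from baseline for continuous laboratory measurements at each visit. SAP 10.3.2 narrows this to descriptive statistics of abnormal post-baseline values plus shifts. The four named liver tests regain a numerical change summary through the liver sentence; ALP does not.

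**3. Missing baseline.** SAP 5.1 defines baseline as the latest value before first dose, and SAP 5.4 uses only data complete for the variable and time point analysed. A subject with no baseline ALP therefore drops out of any shift or change result. Footnote g removes the deviation at every visit in the row. Footnote j still says that last-day safety labs must be collected, and SAP 10.1 still calls the panel required. Amendment 3, which introduced the asterisks, is dated 29 November 2017; SAP v1.1 is dated 14 May 2018.

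**4. Size**

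- Adult excess: 5.2% − 2.9% = 2.3 points; ratio 5.2 / 2.9 = 1.8.
- Expected subjects above 1.5x ULN, assuming adult rates carry over, at the planned 300:100: 300 × 0.052 = 15.6 and 100 × 0.029 = 2.9.
- SAP section 2 says that fewer than a quarter of 400 enrolled, that is, fewer than 100. At 3:1 the ceiling is about 75:25: 75 × 0.052 = 3.9 and 25 × 0.029 = 0.7.
- Solithromycin events with a usable baseline, n × (1 − m) × 0.052, where m is an assumed share with no baseline ALP:

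| m | n = 300 | n = 75 |
|---|---|---|
| 0% | 15.6 | 3.9 |
| 10% | 14.0 | 3.5 |
| 30% | 10.9 | 2.7 |
| 50% | 7.8 | 2.0 |

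**The case against.** The strongest reply is that ALP is not lost. It is a serum chemistry value with a normal range in SAP 10.3.2, so it enters the shift table, the abnormal-results summary, the figures scaled by normal values, the individual graphs and the listing. A reader might infer that the repeat ALP tests get no extreme-value or change display at all. The documents do not support that: worst post-baseline against baseline is shown, and a count above 1.5x ULN could be worked out from listed values and ranges. What is missing is a pre-planned numerical table.

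The omission also follows choices made in the protocol. Section 12.1.3 names AST, ALT and direct bilirubin as the liver tests of special interest, and 14.1.3 gives ALT and AST as examples. No text requires ALP in the liver summary. This stands: the omission is a weak analysis choice rather than a breach of the protocol. But the protocol's list of examples is open, whereas the SAP closes it.

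Three further limits also stand. The adult comparison was with moxifloxacin, which is not among this trial's comparators, so 2.3 points is a reason to look and not a like-for-like benchmark. The asterisks came late and the trial was terminated in March 2018, so they may have affected only late enrolees. With so few subjects, any result is descriptive.

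**Conclusion.** The point holds as an inexpensive gap in the safety analysis. The protocol reports an ALP excess for solithromycin and requests repeat ALP, but no planned table gives its largest increase or the number above 1.5x ULN. At adult rates this concerns about 3.9 solithromycin and 0.7 comparator subjects at the enrolment ceiling. Those counts assume that adult rates apply to children, that the moxifloxacin rate stands in for the comparators, and that the 3:1 split was kept.

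A reader might infer that the waiver singles out baseline and last day. It does not: footnote g covers the whole safety-lab row, and the other three time points are requested on a best-effort basis. Nor is the absence of Day 28 from the liver summary specific to ALP, since that summary stops at Day 16 for every test. How many subjects lack a baseline ALP is unknown, and a waived deviation does not show that the test was skipped. The mismatch between SAP 10.1, SAP Table 4 footnote g and the protocol would be clerical on its own.

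**What to change.** - **SAP 10.3.2, Tables 14.4.3.2.4 and 14.4.3.2.5:** add ALP, with most extreme value, largest increase from baseline, and count above 1.5x ULN. The last item is an addition to the format, since 10.3.2 promises no threshold counts for the four named tests.
- **Same tables:** report by arm the number of subjects with a baseline ALP and with a post-baseline ALP, so that the denominator of any change result is visible.
- **SAP 10.1 and SAP Table 4 footnote g:** align with the current protocol footnote g, and note how it is to be read with footnote j.

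The cost is one analyte from the existing chemistry panel in two tables already planned, plus a few lines of text. No new data are needed. Because the trial has ended, changing the asterisk in the protocol would alter nothing and is not proposed. If the outputs have already been produced, the ALP rows can be added as a descriptive supplement and described as such in the clinical study report, as SAP section 2 provides.

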10.3.2 Day 28 Post Randomization (± 4 days)

1. Every effort should be made to obtain safety labs Day 28 (± 4 days) after the first dose to include ALT, AST, alkaline phosphatase, total and direct bilirubin, and WBC with differential. A separate study sample is not required if these labs are obtained at Day 28 (± 4 days) after the first dose per standard of care.
2. Review and record any SAEs as described in Section 12.1. Every effort should be made to bring the subject back for follow up, but SAEs must be collected via phone/other media if the subject is unable or unwilling to return.

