14.1.3 Safety Analysis

For the primary safety endpoints, the frequency and percentage of subjects with AEs and therapy not tolerated will be determined and 95% CIs calculated. Summaries will be calculated by treatment group for the overall safety population and stratified by age group.

Additional safety analyses include summaries of AEs, descriptive statistics of laboratory values, descriptive statistics of vital signs, and frequency distributions of abnormal physical examinations. Laboratory data, such as hematology and serum chemistry data, as well as safety data will be analyzed. Summary statistics for changes from baseline and shift tables will be presented. Continuous laboratory measurements will be described at each visit using descriptive statistics (mean, median, etc.); observed values and changes from baseline will be summarized. Laboratory tests reflective of liver toxicity (e.g., ALT, AST) will be further summarized in terms of the most extreme values and largest changes from baseline (in the appropriate direction) observed from start of study drug through the end of therapy. All analyses will include summaries for both treatment and active comparator.

Additional details of safety analyses will be included in the Statistical Analysis Plan (SAP).

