12.1.1.1 Reporting of SAEs

All SAEs must be reported to APCER Life Sciences preferably by email within 24 hours of the site's knowledge of the event. APCER contact information:

APCER Email: [contact]

[contact]

[contact]

Amendment #2 16 December 2016

Rationale for Amendment

Amendment 2 incorporates additional safety laboratory evaluations along with new and updated dosing information for all 3 formulations of solithromycin.

Safety laboratories, including ALT, AST, ALP, total and direct bilirubin, and eosinophil count have been added at 72 hours (± 24 hours), Day 16 (± 4 days), and Day 28 (± 4 days). The Day 28 (± 4 days) visit evaluates safety laboratories approximately 3 weeks after completion of dosing, and replaces the Day 36 (± 4 days) visit. Data pertaining to liver laboratory evaluations will be reviewed on a regularly scheduled basis (Section 12.1.3) and presented to the DMC.

Solithromycin suspension dosing information, including the dosage rationale, has been added for all age groups. The IV dose has been updated to 8 mg/kg (maximum 400 mg) for all age groups based on additional Phase 1 pediatric PK data. PK/PD simulations based on adult CABP patient data have been reassessed following an FDA recommendation to remove the loading dose on the first oral dosing day after IV administration; the loading dose did not appear to be required for efficacy but did increase the potential for ALT elevations and could be associated with dosing errors. Consequently, the oral loading dose after IV dosing has been replaced by the daily oral maintenance dose (10 mg/kg; maximum 400 mg). A loading dose will be employed only on the first day of oral only dosing (20 mg/kg; maximum 800 mg).

The duration of dosing with solithromycin will be 5 days with oral only dosing, and 7 days with IV only or IV to oral dosing; previously the duration was 5 to 7 days for all formulations. Five-day oral and 7-day IV and IV to oral regimens of solithromycin were demonstrated to be non-inferior to moxifloxacin in the Phase 3 adult pneumonia studies (CE01-300 and CE01-301). Comparator duration of dosing will continue to be per standard of care.

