		Treatment Days up to Last Day of Treatment ^b	Last Day of Treatment (+48 hours)	Day 16 Post Randomization ^{c, d} (±4 days)	Day 28 Post Randomization ^d (±4 days)
Serious adverse event assessment	X	X	X	X	X
Clinical outcomes and symptom assessments: Early Clinical Response, End of Treatment, and Follow-Up Post Treatment ^f	X	X ^u	X ^v	X ^w	

- a Screening/baseline can occur up to 72 hours prior to randomization. Standard-of-care laboratory data and radiological imaging from up to 72 hours prior to randomization may be used as screening procedures. Screening/baseline and first day of treatment may be the same day.
- b Treatment period is 5 to 7 days for solithromycin and 5 to 10 days for comparators. These assessments and procedures may be done prior to Day 3 if the subject is discharged from the hospital before Day 3.
- c Record vital signs for each day available. Physical examinations should be recorded from baseline and the Day 3 to 4 visit (early clinical outcome assessment) and at the Last Day of Treatment visit.
- d Every effort should be made to bring the subject back. If the subject is unable or unwilling to return, the AEs/SAEs must be collected via telephone/other media.
- e Vital signs taken at the closest time post-drug administration should be noted. If vital signs following drug administration are not available, record the first value of the day.
- f Screening chest x-ray does not need to be repeated if a standard-of-care chest x-ray was performed within 72 hours of randomization. Subjects that are outpatient and starting on oral therapy do not need a screening x-ray.
- g Local laboratory; includes hemoglobin, hematocrit, white blood cell count with differential, platelet count, blood urea nitrogen, calcium, serum creatinine, potassium, sodium, aspartate aminotransferase, alanine aminotransferase, alkaline phosphatase, total and direct bilirubin, and albumin.
- h A separate study sample is not required if safety labs above are obtained at baseline per standard of care. If multiple laboratory tests are obtained within 72 hours of randomization, record test results closest to randomization.
- i Every effort should be made to obtain safety labs to include aspartate aminotransferase, alanine aminotransferase, alkaline phosphatase, total and direct bilirubin, and white blood cell count with differential. A separate study sample is not required if safety labs above are obtained within the visit window per standard of care.

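### The SAP's liver summary of worst values and largest increases stops at Day 16, so the scheduled Day 28 liver tests cannot enter it

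*SAP*

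**What the plan says.** SAP Section 10.3.2 singles out ALT, AST, and total and direct bilirubin for a further summary of the "most extreme values and largest increases from baseline observed from the start of study drug through Day 16 Post-Randomization" (± 4 days). The corresponding tables in SAP Section 12, Tables 14.4.3.2.4 and 14.4.3.2.5, carry no window in their titles, so the text of 10.3.2 governs.

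Liver tests are scheduled later than that. Protocol Section 10.3.2 states: "Every effort should be made to obtain safety labs Day 28" (± 4 days), and names the liver tests. In the SAP, footnote i to Table 4 in Section 4 applies to the Day 28 column and reads: "Every effort should be made to obtain safety labs to include aspartate aminotransferase, alanine aminotransferase, alkaline phosphatase, total and direct bilirubin". SAP Section 10.1 likewise records that these labs are sought "at the Day 16 and Day 28 post-randomization visits (implemented in Protocol version 3.0"). The rationale for Amendment 2, in Protocol Appendix A, gives the purpose of the late draw: the Day 28 "visit evaluates safety laboratories approximately 3 weeks after completion of dosing".

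Protocol Section 14.1.3 plans the same kind of liver summary over a shorter period, "observed from start of study drug through the end of therapy".

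**The concern.** The late draw was added to see liver values well after dosing, yet the one summary dedicated to liver toxicity closes before it. The SAP acknowledges the Day 28 labs and gives no reason for leaving them out of that summary.

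The liver is this drug's known safety signal. Protocol Section 5.2.4.1 reports ALT above 3×ULN in 7.2% of adults on solithromycin against 3.6% on moxifloxacin in the pooled Phase 3 trials, with evidence of an exposure-response relationship. Adverse event tables are not a reliable backstop. Under Protocol Section 12.1 a laboratory abnormality without symptoms or intervention is generally not an adverse event, and SAP Section 10.3.1 collects non-serious events only through Day 16 (± 4 days). A silent rise at Day 28 would show only in laboratory outputs.

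At stake is the accuracy of the reported maximum and largest increase for any child who peaks late. The report could also disagree with itself. If the worst-value figures use all post-baseline draws, as their titles read, the figure would show a higher maximum than the liver table for the same child.

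**Working it through.** No stated figure in the plan bears on this summary, so the check compares the visit windows and then looks for another output that would fill the gap.

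**Scheduled post-baseline liver draws** (Protocol Sections 10.2.1, 10.2.2, 10.3.1 and 10.3.2; SAP Section 10.1 and Table 4):

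1. 72 hours (± 24 hours) after first dose
2. Last day of treatment (+48 hours)
3. Day 16 (± 4 days)
4. Day 28 (± 4 days)

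The SAP 10.3.2 window covers draws 1 to 3, or 3 of 4. The Protocol 14.1.3 window covers draws 1 and 2, or 2 of 4, counting the last-day draw as within therapy.

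**Overlap.** Day 16 window: 16 − 4 = 12 to 16 + 4 = 20. Day 28 window: 28 − 4 = 24 to 28 + 4 = 32. The smallest gap is 24 − 20 = 4 days, with days 21 to 23 in neither window. The body of Protocol Section 10.3.2 counts Day 28 from first dose, not randomization. If first dose falls 0 to 3 days after randomization (an assumption), the earliest Day 28 draw moves to day 24 to 27, which is further from the cut-off.

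**Days after last dose**, taking the last dose on the day equal to the course length:

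| Course | Day 16 draw | Day 28 draw |
|---|---|---|
| 5 days | 12 − 5 = 7 to 20 − 5 = 15 (nominal 11) | 24 − 5 = 19 to 32 − 5 = 27 (nominal 23) |
| 7 days | 5 to 13 (nominal 9) | 17 to 25 (nominal 21) |
| 10 days (longest comparator course) | 2 to 10 (nominal 6) | 14 to 22 (nominal 18) |

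Each entry may shift by one day according to whether randomization is day 0 or day 1. For solithromycin the summary therefore reaches at most 13 or 15 days past the last dose. The period the Day 28 draw was meant to observe is absent.

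**Where a Day 28 value can still appear.** SAP Sections 10.3.2 and 12 also plan an abnormal-results table, a shift table to worst post-baseline value, worst-versus-baseline figures scaled by normal values, individual graphs and graded listings. None states a Day 16 limit. The shift table records only Normal or Abnormal, so it gives no magnitude. The figures, graphs and listings do show magnitude.

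**Whether another table gives the Day 28 increase.** Protocol Section 14.1.3 says continuous laboratory measurements will be "described at each visit using descriptive statistics (mean, median, etc.); observed values and changes from baseline will be summarized". SAP Section 10.3.2 is narrower: "Descriptive statistics will be generated for post-baseline abnormal laboratory data". No title in SAP Section 12 names a by-visit change table. No planned table is therefore stated to give the increase from baseline at Day 28.

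**The case against.** The strongest reply is that no commitment is broken. The protocol ends this summary at the end of therapy, and the SAP already extends it. Day 16 also fits the rest of the safety plan. It is the SAP's cut-off for non-serious adverse events (Sections 10.2 and 10.3.1) and the last visit with physical examination, vital signs and outcome assessment. SAP Section 2 names no individual curtailed analysis, so its silence on this window proves nothing.

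The practical loss is also limited. Enrolment stopped below one quarter of 400, so under 100 children across both arms, and every recorded value can be read from the listings. The worst-versus-baseline figures let a reader judge the increase even though it is not tabulated. Only titles are available, so a different window in a table shell cannot be ruled out. The count of 3 of 4 draws describes planned slots, and every draw except the last-day one is on a best-effort basis.

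These points stand, and they limit the finding to one summary and a minor grade. They do not remove it. Agreement with the adverse event cut-off is a plausible motive that the SAP does not state. It also does not suit a laboratory summary whose last scheduled draw was added for late liver surveillance.

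**Conclusion.** The concern holds, as a minor one. Read as written, SAP Section 10.3.2 keeps every in-window Day 28 result out of the liver summary and would understate the maximum and largest increase for any child whose peak falls there. Confidence in the window itself is high. The mismatch between table and figure is conditional on the figures using all post-baseline draws.

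The numerical effect is unknown, because the documents give neither the number of Day 28 draws nor the share of children who peak then. It is probably small: Protocol Section 5.2.4.1 describes adult elevations as usually symptom-free and reversible. That inference assumes children behave as adults did. In-trial liver monitoring under Protocol Section 12.1.3 covers any post-baseline visit and is unaffected.

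**What to change.** In SAP Section 10.3.2, define the extreme-value and largest-increase summary over all post-baseline draws through the Day 28 (± 4 days) visit, and apply that to Tables 14.4.3.2.4 and 14.4.3.2.5. Add a row with the number of subjects who have a Day 28 draw, by arm. Describe the difference from Protocol Section 14.1.3 in the study report, the route SAP Section 2 provides for deviations.

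The cost is one cut-off and one count row in two tables, with no new data. The drawback is uneven follow-up. Day 28 labs are best-effort and began with protocol version 3.0, as did the 72-hour and Day 16 labs, and Day 28 safety contact may be by telephone. A maximum through Day 28 therefore rests on more draws for some children than for others, and the count row makes that visible.
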